1.2.5.2. Immunology Parameters

The secondary immunology endpoint is the Flow Cytometry response magnitudes at baseline and Week 27 visits.

Exploratory immunology endpoints include the following:

- Assessment of pro-inflammatory and immunosuppressive elements in vulvar tissue, which may include visualization of PD-L1, Granulysin, perforin, CD137, CD103, and possibly other relevant markers.
- Levels of serum anti-HPV-16 and antiHPV-18 antibody concentrations at baseline, Weeks 15, 27, 48, 74, and 96 visits.
- Interferon-γ ELISpot response magnitudes at baseline and Weeks 15, 27, 48, 74 and 96 visits.
- Immunohistochemistry biomarker results including but not limited to, CD8+ and FoxP3+ infiltrating cells as well as assessment of cell death via Cleaved Caspase 3 assessment.

1.2.5.3. Safety Parameters

Safety evaluations performed during the study include physical examinations, measurement of vital signs, and monitoring of AEs, injection site reactions, pain, and concomitant medications.

Secondary safety endpoints include the following:

- Local and systemic events for 7 days following each dose as noted in the Participant Diary
- All adverse events including SAEs, AESIs, SUSARs, UADEs, and other unexpected AEs for the duration of the study (through Week 100 visit)

Treatment-emergent adverse events (TEAEs) are collected throughout study. All TEAEs that occur within 7, 14, or 28 days following each injection will be summarized separately.

2. SUBJECT POPULATION

2.1. **Population Definitions**

The following subject populations will be evaluated and used for presentation and analysis of the data:

- Modified Intention-to-Treat (mITT) Population: All subjects who receive at least 1 dose of VGX-3100 + EP and who have the analysis endpoint of interest. Subjects in this sample will be grouped to treatment arms as randomized.
- Per-protocol (PP) Population: All subjects who receive at least 4 doses of VGX-3100 + EP, have no protocol violations, and who have the analysis endpoint of interest. Subjects in this sample will be grouped to treatment arms as randomized. Subjects excluded from the PP population will be identified and documented prior to locking of the study database.
- Safety Population: All subjects who receive at least 1 dose of VGX-3100 (with or without EP). Subjects will be analyzed as to the treatment they received.

The mITT population is the primary population for the analysis of efficacy parameters. The PP population will be considered supportive of the corresponding mITT population for the analysis of efficacy. The Safety population is the primary population for the analysis of safety endpoints.

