3. GENERAL STATISTICAL METHODS

3.1. Sample Size Justification

The study will enroll 36 subjects randomized to receive either 6 mg VGX-3100 or 6 mg VGX-3100 plus imiquimod, IM followed by EP in a 2:1 ratio. This sample size provides 80% power to declare each arm superior to historical control with a 1-sided 0.025 type 1 error level for each hypothesis, assuming the true proportion of subjects who achieve the primary endpoint is 20% and 28% for the respective treatment arms and 2% for the historical control, and that 90% of subjects in each treatment group are evaluable at Week 48 from randomization.

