4.2. Demographics and Baseline Characteristics

Demographics and baseline characteristics will be summarized and presented by treatment group and overall. Age, height, weight, and BMI will be summarized using descriptive statistics (number of subjects, mean, SD, median, minimum, and maximum). The number and percentage of subjects in each randomization stratum, ethnicity category, race category, and country also will be presented. Results at screening for VIN category, HPV type, years of education, and type of insurance will also be presented.

Abnormal medical history will be summarized by term as collected on the electronic CRF. Prior vulvar disease, HPV diagnoses, and reproductive history will be presented in data listings as well as tobacco history and alcohol use.

No formal statistical comparisons between groups will be performed for demographics, baseline data, or medical history data. Data for each subject will also be provided in data listings.

Relevant Output

| Table 14.1.2.1A | Demographics and Baseline Characteristics (mITT/Safety Population) |
|------------------|--------------------------------------------------------------------|
| Listing 16.2.4.1 | Demographics and Baseline Disease Characteristics |
| Listing 16.2.4.2 | Abnormal Medical History |
| Listing 16.2.4.3 | Prior Vulvar Disease and HPV Diagnoses |
| Listing 16.2.4.4 | Reproductive System History |
| Listing 16.2.4.5 | Alcohol, Tobacco, and Recreational Drug Use |
| | |

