4.3.1. Primary Efficacy Endpoint

The primary efficacy endpoint is the combined outcome of histologic regression of vulvar HSIL and virologic clearance of HPV-16/18 at Week 48. Histologic regression is defined as no histologic evidence of vulvar HSIL (normal tissue or vulvar LSIL (VIN 1) or condyloma) at Week 48. Virologic clearance is defined as clearance of HPV 16 or 18 at Week 48. A subject achieves the primary outcome (i.e., is a "responder") if histologic regression and virologic clearance is observed at Week 48 and the subject did not receive any non-study related treatment for vulvar HSIL. A subject is a non-responder if there is histologic evidence of vulvar HSIL or vulvar carcinoma, or evidence of HPV-16/18, or subject received non-study related treatment for vulvar HSIL.

| Table 4-1: | Definition | of Responder | and Non-Responder |
|------------|------------|--------------|-------------------|
|------------|------------|--------------|-------------------|

| Responder | Non-Responder | | |
|-----------------------------------------------------------------------------------------------------------------------------|--------------------------------------------------------------------------------------------------------------|--|--|
| • Subject with no histologic evidence of vulvar HSIL | • Subject with histologic evidence of vulvar HSIL or vulvar carcinoma at evaluation | | |
| AND | OR | | |
| Subject with no evidence of HPV-16 or HPV-18 in vulvar tissue at evaluation AND | Subject with evidence of HPV-16 or HPV-18 in vulvar tissue at evaluation OR | | |
| • Subject did not receive any non-study related treatment for vulvar HSIL | • Subject who received non-study related treatment for vulvar HSIL | | |
| Note: The efficacy time frame is defined by samples obtained any time starting from 14 days prior to the protocol-specified | | | |

target date of Week 48. The first such sample determines the histology endpoint. The most recent HPV clearance result prior to time of the histology sample within the time frame determines the HPV clearance endpoint.

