4.3.2. Secondary and Exploratory Efficacy Endpoints

Secondary and exploratory efficacy endpoints are supportive to the primary hypothesis.

The following secondary and exploratory efficacy binary endpoints will be presented as percentage point estimates and exact Clopper-Pearson 95% CIs. Each of the following endpoints will be analyzed separately based on qualifying lesions present at baseline and for all lesions regardless of presence at baseline, unless otherwise noted.

- Histologic regression of vulvar HSIL or virologic clearance of HPV-16/18 in vulvar tissue will be assessed at Weeks 74 and 96 by treatment group for all subjects and stratified by subjects who receive 4 or 5 doses (Week 74) and 4, 5, or 6 doses (Week 96).
- Histologic regression of vulvar HSIL will be assessed at Week 48 by treatment group.
- Virologic clearance of HPV-16/18 in vulvar tissue will be assessed at Week 48 by treatment group.
- Histologic regression of vulvar HSIL will be assessed at Weeks 74 and 96 by treatment group for all subjects and stratified by subjects who receive 4 or 5 doses (Week 74) and 4, 5, or 6 doses (Week 96).
- Virologic clearance of HPV-16/18 in vulvar tissue will be assessed at Weeks 74 and 96 by treatment group for all subjects and stratified by subjects who receive 4 or 5 doses (Week 74) and 4, 5, or 6 doses (Week 96).
- Histologic regression of vulvar HSIL to normal tissue will be assessed at Week 48 by treatment group. Normal tissue is defined as having no evidence of vulvar HSIL, no evidence of LSIL (VIN1), and no evidence of condyloma.
- Non-progression of vulvar HSIL to vulvar cancer will be investigated at Week 48 by treatment group. Progression is defined as advancement to carcinoma by histology according to the Pathology Adjudication Committee.
- Virologic clearance of HPV-16/18 outside of the vulva will be assessed at Week 48 by treatment group (for qualifying lesions only) and be presented by anatomic location (cervical, intra anal, oral, and vaginal).
- Histologic regression of vulvar HSIL or virologic clearance of HPV-16/18 in vulvar tissue will be assessed at Weeks 48, 74, and 96 by treatment group.

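### The primary mITT set admits only treated subjects who have the endpoint, and no analysis keeps all treated subjects, so response rates may be too favourable

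*SAP*

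**What the plan says.** SAP section 2.1 defines mITT as "All subjects who receive at least 1 dose of VGX-3100 + EP and who have the analysis endpoint of interest" and adds that "The mITT population is the primary population for the analysis of efficacy parameters". The per-protocol set also requires the endpoint, along with at least four doses and no violations. Section 4.3 names no other efficacy set.

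Section 3.1 plans for 90% of each arm to be evaluable at Week 48. Section 3.9 does not replace withdrawals. Section 3.10 deals with partial dates for adverse events and medications only, and says nothing about a missing histology or HPV result.

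Three other places bear on who has the endpoint:

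- Section 4.3.1 and Table 4-1 list "Subject who received non-study related treatment for vulvar HSIL" as a non-responder category in its own right, joined to the others by OR, with no sample required.
- Section 4.3.2 says "Non-progression of vulvar HSIL to vulvar cancer will be investigated at Week 48 by treatment group", while section 1.2.5.1 defines that endpoint cumulatively, from baseline to the Week 48 visit.
- Section 3.11 and the note to Table 4-1 open the efficacy window 14 days before the Week 48 target date. Section 3.11 limits the window to histologic regression and virologic clearance.

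**The concern.** A set conditioned on having the outcome is an observed-case set, whatever its label, and its membership changes from endpoint to endpoint. Each arm is compared with a fixed historical 2%, so no concurrent untreated arm loses subjects in the same way and offsets the exclusion. A subject who withdraws without a Week 48 sample and without known outside treatment simply disappears from the rate.

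The per-protocol analysis cannot reveal the effect, because it applies the same filter. Section 5 of the SAP reports no departures from the protocol's analyses, so the SAP gives no sign that another rule exists elsewhere. At stake are the point estimates, confidence intervals and p-values, which are the main product of a 36-subject Phase 2 study.

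**Working it through.** **Inputs.** All come from the SAP: arms of 24 and 12 (section 1.2.1); "1-sided 0.025 type 1 error level for each hypothesis"; 20% and 28% assumed response, 2% historical control and 90% evaluable (section 3.1); exact binomial test, Clopper-Pearson interval, success if p < 0.025 and the lower limit exceeds 0.02 (section 4.3.1).

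**Step 1: the plan's own power.** The SAP states "This sample size provides 80% power to declare each arm superior to historical control". The critical count is the smallest r with P(X ≥ r | n, 0.02) ≤ 0.025, and power is P(X ≥ r | n, p1). Evaluable numbers are 0.9 × 24 = 21.6 and 0.9 × 12 = 10.8.

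| Arm | n | r | Power |
|---|---|---|---|
| Alone, p1 = 0.20 | 21 | 3 | 82.1% |
| Alone, p1 = 0.20 | 22 | 3 | 84.6% |
| With imiquimod, p1 = 0.28 | 10 | 2 | 81.7% |
| With imiquimod, p1 = 0.28 | 11 | 2 | 85.8% |

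The stated 80% is reproduced as at least 80%.

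**Step 2: size of the overstatement.** Let x be the responders, m the evaluable subjects and N the treated subjects. The plan reports x/m. If all missing subjects are non-responders, the all-treated rate is x/N, and the ratio of the two is N/m. At 90% evaluable this is 1/0.9 = 1.11.

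| Observed-case | All treated, missing = non-response |
|---|---|
| 4/22 = 18.2% (CI 5.2 to 40.3), p = 0.0009 | 4/24 = 16.7% (CI 4.7 to 37.4), p = 0.0012 |
| 3/11 = 27.3%, p = 0.0012 | 3/12 = 25.0%, p = 0.0015 |
| 2/10 = 20.0%, p = 0.0162 | 2/12 = 16.7%, p = 0.0231 |

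**Step 3: effect on the decision.** The critical count is 3 for every n from 13 to 31 and 2 for every n from 2 to 12. With a given number of responders, the two denominators can disagree only if 12 or fewer of the 24 VGX-3100-alone subjects are evaluable. In the 12-subject arm they never disagree: even 2/12 has p = 0.0231 and lower limit 0.0209, which still meets both criteria.

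**Step 4: type I error.** Suppose the true all-treated rate is 2% and every missing subject is a non-responder. The rate among evaluable subjects is then 0.02 × 24/22 = 0.0218 or 0.02 × 12/11 = 0.0218. The chance of a false success is 0.0117 (n = 22) and 0.0230 (n = 11), against 0.0118 and 0.0231 with full denominators.

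**Step 5: power if missing counts as non-response.** Section 3.1 does not say whether 20% and 28% refer to evaluable or to all treated subjects. If to evaluable subjects, the all-treated rates are 0.9 × 0.20 = 0.18 and 0.9 × 0.28 = 0.252:

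- P(X ≥ 3 | 24, 0.18) = 83.3%
- P(X ≥ 2 | 12, 0.252) = 84.5%

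If they already refer to all treated subjects, power is 88.5% and 89.0%.

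**The case against.** The best defence is that the success criterion is unaffected at any plausible level of missingness and that intervals such as 5.2 to 40.3 and 4.7 to 37.4 overlap almost entirely. The window also has no stated upper limit, so late samples count and missingness may be lower than planned. All of that stands, and it limits the severity. It does not supply an all-treated estimate or a rule for missing results.

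Three stronger readings are tempting, and the SAP does not support them.

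- *Early failures in general leave the denominator.* Table 4-1 already makes outside treatment a non-response without requiring a sample. The subject clearly lost is one with neither a sample nor known outside treatment. Section 2.1 does not say that outside treatment counts as having the endpoint, so the two sections need reconciling.
- *Early cancers drop out of the non-progression analysis.* Section 1.2.5.1 counts progression from baseline to Week 48, the 14-day window does not extend to that endpoint, and note 9 to Table 1-1 sends all biopsies taken up to an in-person discharge visit to the Pathology Adjudication Committee. An early confirmed carcinoma is most naturally already an event. The wording in section 4.3.2 leaves enough doubt for one clarifying sentence.
- *The title of Table 14.1.2.1A, "Demographics and Baseline Characteristics (mITT/Safety Population", shows that the two sets are confused.* It is a table title, its shell is in a separate document, and no efficacy result depends on it.

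**Conclusion.** The point holds as one about estimation. As written, the SAP yields observed-case response rates against a fixed 2%, has no rule for a missing Week 48 result, and has no analysis that retains all treated subjects.

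The direction of bias is conditional. The rates are too high if dropouts respond less often than completers, and the 1.11-fold figure is the upper bound at the planned 90% evaluable, reached when every missing subject is a non-responder. The SAP gives neither reasons for dropout nor the way missing outcomes entered the historical 2%, so it cannot be said that the rates are overstated as a matter of fact.

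Nor should a reader infer that the superiority claim is unsafe or that type I error is inflated; the checks show neither. Severity: should fix.

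**What to change.** Amend the SAP as follows:

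1. Define mITT as all randomized subjects who received at least one dose of VGX-3100 with electroporation, grouped as randomized.
2. For regression, clearance and combined endpoints at Week 48, count a missing result as non-response.
3. State that non-study treatment for vulvar HSIL, or carcinoma confirmed by the Pathology Adjudication Committee at any time up to Week 48, counts as an available and failed endpoint. This aligns section 2.1 with section 4.3.1, Table 4-1 and section 1.2.5.1.
4. Keep the present observed-case set as a sensitivity analysis.

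The cost is a few sentences of SAP text, one extra table set and slightly lower reported rates. Power remains above the stated 80%.

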2.2. Protocol Violations

At the discretion of the Sponsor, protocol violations, as determined by a review of the data prior to locking of the study database and the conduct of statistical analyses, will result in the removal of a subject's data from the PP population. The Sponsor or designee will be responsible for producing the final protocol violation file (formatted as a Microsoft Excel file), in collaboration with Veristat and the data monitoring group as applicable; this file will include a description of the protocol violation which warrant exclusion from the PP population. This file will be finalized prior to hard database lock.

All protocol violations will be presented in a data listing.

Relevant Output

Listing 16.2.2.2 Protocol Violations

3. GENERAL STATISTICAL METHODS

3.1. Sample Size Justification

The study will enroll 36 subjects randomized to receive either 6 mg VGX-3100 or 6 mg VGX-3100 plus imiquimod, IM followed by EP in a 2:1 ratio. This sample size provides 80% power to declare each arm superior to historical control with a 1-sided 0.025 type 1 error level for each hypothesis, assuming the true proportion of subjects who achieve the primary endpoint is 20% and 28% for the respective treatment arms and 2% for the historical control, and that 90% of subjects in each treatment group are evaluable at Week 48 from randomization.

3.2. General Methods

All data listings that contain an evaluation date will contain a relative study day (Rel Day). Pretreatment and on-treatment study days are numbered relative to the day of the first dose of study medication (Day 0) which is designated as Rel Day 1. The preceding day is Rel Day -1, the day before that is Rel Day -2, etc. There is no Rel Day 0.

All output will be incorporated into Microsoft Word or Excel files, or Adobe Acrobat PDF files, sorted and labeled according to the International Conference on Harmonisation (ICH) recommendations, and formatted to the appropriate page size(s).

Tabulations will be produced for appropriate demographic, baseline, efficacy, immunogenicity, and safety parameters. For categorical variables, summary tabulations of the number and percentage of subjects within each category of the parameter will be presented. For continuous variables, the number of subjects, mean, median, standard deviation (SD), minimum, and maximum values will be presented. Summarizations will be presented by treatment grouping and overall as applicable.

Formal statistical hypothesis testing will be performed on the primary endpoint for each treatment group compared to historical control separately at a 1-sided, 0.025 level of significance. Summary statistics will be presented, as well as 2-sided 95% confidence intervals (CIs) on selected efficacy and safety parameters, as described in the sections below.

3.3. Computing Environment

All statistical analyses will be performed using SAS statistical software Version 9.3 or higher, unless otherwise noted. Adverse events will be coded using the current Medical Dictionary for Regulatory Activities (MedDRA), starting with Version 20.0.

3.4. Baseline Definitions

For all analyses, baseline will be defined as the most recent measurement prior to the first administration of study drug.

3.5. Methods of Pooling Data

Data will be pooled across study sites.

3.6. Adjustments for Covariates

No formal statistical analyses that adjust for possible covariate effects are planned.

3.7. Multiple Comparisons/Multiplicity

No adjustments for multiple testing will be implemented, as 2 one-sided tests will each utilize a type I error rate of 2.5% on testing the primary hypothesis.

3.8. Subpopulations

Certain subgroups will be analyzed separately at additional time points for effectiveness of additional doses and/or surgical treatments.

- Subgroups A and B Subjects with no HSIL at Week 48 will receive 4 doses.
- Subgroups C and D Subjects with HSIL at Week 48, who have a reduction in lesion size or no increase in lesion size from baseline, may receive a fifth dose of VGX-3100 administered IM with EP at Week 52 per the judgment of the Investigator. Subjects with HSIL at Week 74 may receive a sixth dose of VGX-3100 administered IM with EP at Week 78 per the judgment of the Investigator.
- Subgroup E Subjects may receive surgical treatment per the judgment of the Investigator.

3.9. Withdrawals, Dropouts, Loss to Follow-up

Subjects who are withdrawn or discontinue from the study will not be replaced.

3.10. Missing, Unused, and Spurious Data

When tabulating AE data, partial dates will be handled as follows in order to determine treatment emergence. If any of the day, month, or year is missing, the onset date will be set to the earliest date that is consistent with any non-missing date information, unless the non-missing date information is the same as study treatment start. In this case, in order to conservatively report the event as treatment-emergent, the onset date will be assumed to be the date of start of treatment. A completely missing onset date will be coded as the day of start of treatment.

A prior medication is defined as any medication that has a stop date before the start of the trial (prior to Dose #1 on Day 0). A concomitant medication is defined as any medication that has a stop date that is on or after the date of first dose of study drug. For prior and concomitant medications, partial start dates will not be imputed, as stop dates determine prior versus concomitant. Partial stop dates will be assumed to be the latest possible date consistent with the partial date.

3.11. Visit Windows

It is expected that all visits should occur according to the protocol schedule. All data will be tabulated per the evaluation visit as recorded on the CRF even if the assessment is outside of the visit window. In data listings, the relative day of all dates will be presented.

The efficacy time windows for histologic regression and virologic clearance are defined by samples obtained any time starting from 14 days prior to the protocol-specified target date of visit.

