1.1.3. Study Objectives

1.1.3.1. Primary Objective

The primary objective is to determine the efficacy of 4 doses of VGX-3100, alone or in combination with imiquimod, with respect to combined histopathologic regression of vulvar HSIL and virologic clearance of HPV-16/18 in vulvar tissue.

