Subjects in Subgroups C and D may receive a fifth and possibly a sixth dose at Week 52 and Week 78, respectively.

To assess quality of life and related impacts on subjects, PRO instruments will be provided and will include the Short Form Health Survey version 2 (SF-36v2TM), the EQ-5D-5L (EuroQol Research Foundation), WOMAN-PRO (WOMen with vulvAr Neoplasia) Clinical Trial Version 2.0, and 2 additional PRO questions assessing quality of life after surgery or biopsy.

The total duration of the study is up to 10 weeks for the screening period and up to100 weeks for the treatment and follow-up periods. The study duration is reduced to 78 weeks for subjects that have not already completed the Week 78 visit.

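### The Week 48 efficacy window has no end date, so a Week 74 biopsy can become the Week 48 primary result of a subject without a Week 48 sample, against the SAP's own CRF-visit rule

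*SAP*

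**What the plan says.** - **Purpose.** Section 1.1.3.1: "The primary objective is to determine the efficacy of 4 doses of VGX-3100, alone or in combination with imiquimod". The primary endpoint is read at Week 48.
- **Window.** Section 3.11 defines the histology and virology windows as "defined by samples obtained any time starting from 14 days prior to the protocol-specified target date of visit". The note to Table 4-1 (section 4.3.1) does the same for Week 48: "The efficacy time frame is defined by samples obtained any time starting from 14 days prior to the protocol-specified" Week 48 target date. Both state a start and no end.
- **Which sample counts.** Table 4-1 note: "The first such sample determines the histology endpoint". For virology: "The most recent HPV clearance result prior to time of the histology sample within the time frame determines the HPV clearance endpoint".
- **Competing rule.** The paragraph before the window definition in section 3.11 says: "All data will be tabulated per the evaluation visit as recorded on the CRF even if the assessment is outside of the visit window".
- **Additional dosing.** Section 3.8, on who is eligible for the fifth dose: "Subjects with HSIL at Week 48, who have a reduction in lesion size or no increase in lesion size from baseline, may receive" it. Section 1.2.1 says Subgroups C and D "may receive a fifth and possibly a sixth dose at Week 52 and Week 78, respectively".
- **Population.** Section 2.1 limits mITT, the primary efficacy population, to dosed subjects who have the endpoint being analysed.
- **Schedule.** Table 1-1 lists biopsies at screening and Weeks 48, 74 and 96. The tolerance is ±7 days at Week 48 and ±14 days at Weeks 52, 74 and 96.

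**The concern.** A window that opens and never closes, combined with a first-sample rule, gives every subject with any later biopsy a Week 48 result. If the Week 48 biopsy is missing, the next scheduled one is at Week 74. The primary endpoint would then credit a response about half a year late as a Week 48 response. It would also decide who is in the denominator, because having the endpoint is a condition of mITT membership.

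The CRF-visit sentence gives the opposite assignment for the same biopsy. Two programmers following section 3.11 could therefore produce different primary tables. The trial is open-label and each arm's claim turns on two or three responders, so that choice should not remain open until the data are known.

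**Working it through.** **1. Calendar** (7-day weeks from Day 0; tolerances from Table 1-1)

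| Event | Days |
|---|---|
| Week 48 target | 48 × 7 = 336 |
| Efficacy window opens | 336 − 14 = 322 |
| Week 48 visit | 329 to 343 |
| Week 52 visit (possible fifth dose) | 364 ± 14 = 350 to 378 |
| Week 74 biopsy | 518 ± 14 = 504 to 532 |
| Efficacy window closes | not stated |

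A Week 74 biopsy falls (504 − 336)/7 = 24 to (532 − 336)/7 = 28 weeks after the Week 48 target, and is still inside the window.

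**2. Assignment under the two rules**

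| Subject | Date rule with first sample | CRF-visit rule |
|---|---|---|
| Week 48 biopsy on or after day 322 | that biopsy | that biopsy, if recorded as Week 48 |
| No Week 48 biopsy, Week 74 biopsy taken | Week 74 biopsy is the Week 48 result; in mITT | no Week 48 result; not in mITT |
| Week 48 biopsy before day 322, Week 74 biopsy taken | Week 74 biopsy is the Week 48 result | the early biopsy |

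The rules disagree in the second and third rows.

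**3. The plan's own figure.** Section 3.1 states 80% power per arm with 36 subjects (24 and 12 by section 1.2.1), true rates of 20% and 28% against 2%, one-sided 0.025, and 90% evaluable. With an exact binomial test, the critical count r is the smallest with P(X ≥ r | n, 0.02) < 0.025.

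- VGX-3100 alone: n = 20 gives 79.4% power; n = 21 (r = 3, alpha 0.0081) gives 82.1%. 21/0.9 = 23.3, rounded up to 24.
- Combination: n = 9 gives 76.6%; n = 10 (r = 2, alpha 0.0162) gives 81.7%. 10/0.9 = 11.1, rounded up to 12.
- Total 36, as stated, reading 80% as at least 80%.

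**4. Effect of one late responder.** Without the late sample she is outside mITT, so both numerator and denominator rise by one.

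- Combination, 1/10: p = 1 − 0.98^10 = 0.183; Clopper-Pearson lower limit 0.0025. Fails.
- Combination, 2/11: p = 1 − 0.98^11 − 11(0.02)(0.98^10) = 1 − 0.8007 − 0.1798 = 0.0195; lower limit 0.0228. Succeeds.
- VGX-3100 alone, 2/21: p = 1 − 0.98^21 − 21(0.02)(0.98^20) = 1 − 0.6543 − 0.2804 = 0.065; lower limit 0.0117. Fails.
- VGX-3100 alone, 3/22: p = 1 − 0.98^22 − 22(0.02)(0.98^21) − 231(0.02²)(0.98^20) = 0.0093; lower limit 0.0291. Succeeds.

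**5. Type I error, as an illustration.** Assumption: one subject has only a late sample with response rate q, and all others respond at 2%. For the combination arm at n = 11, the chance of success is (1 − q) × P(X ≥ 2 | 10) + q × P(X ≥ 1 | 10).

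- q = 2%: 0.0195
- q = 5%: 0.0245
- q = 10%: 0.9 × 0.0162 + 0.1 × 0.1829 = 0.033
- q = 20%: 0.8 × 0.0162 + 0.2 × 0.1829 = 0.050

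The nominal level is 0.025. For VGX-3100 alone at n = 22, the values at q = 5%, 10% and 20% are 0.011, 0.014 and 0.020, so one such subject does not break the level there. The SAP gives no value for q.

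**The case against.** A reader might infer that a Week 74 biopsy after a fifth dose would routinely replace a failed Week 48 result. The SAP does not support that. Section 3.8 ties the fifth dose to HSIL at Week 48, so a subject dosed as planned already has Week 48 histology. If that sample falls on or after day 322, the first-sample rule fixes her as a non-responder. The post-dose route is left only for exceptions, such as a Week 48 biopsy taken more than 14 days early (beyond the ±7-day tolerance) or one that cannot be evaluated. Nor does the window turn a valid Week 48 failure into a response. A late sample must also clear both histology and HPV, and a subject who received non-study treatment for vulvar HSIL stays a non-responder.

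The CRF-visit sentence is also a real counterweight: read alone, it keeps a Week 74 biopsy at Week 74. So it is not settled that such a biopsy would be counted at Week 48. What stands is that section 3.11 gives two rules with different answers, and that the more specific one, repeated under the primary endpoint, produces the wrong one.

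The arithmetic shows how sensitive the test is to one subject, not how often misassignment occurs. The 90% evaluable assumption implies about 24 × 0.1 = 2.4 and 12 × 0.1 = 1.2 subjects without a Week 48 endpoint. How many of them would have a later biopsy cannot be known from the document.

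The Week 74 window is likewise open against Week 96, but this touches exploratory endpoints only. It is limited further by the stratification by doses received (section 4.3.2), the shortening of the study to 78 weeks, and the withdrawal of the sixth dose after Amendment 5.0 (Table 1-1, footnote 13).

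**Conclusion.** The point holds for subjects without a usable Week 48 sample. As written, the window and first-sample rules can assign a biopsy taken 24 to 28 weeks late to the Week 48 primary endpoint and admit the subject to mITT. Another sentence in the same section says the opposite, and no precedence is stated. One such responder is enough to reverse either arm's conclusion at the planned evaluable numbers (10 to 11 and 21 to 22). That rests on the arm being one responder short of its critical count; the frequency is unknown.

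The stronger claim, that post-fifth-dose samples generally stand in for Week 48 results, does not hold: sections 3.8 and 4.3.1 together confine it to exceptions. This should be fixed before database lock, but it does not call the design or the sample size into question.

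**What to change.** In section 3.11 and the note to Table 4-1:

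1. Give each efficacy window an end that falls before any additional dose and before the next scheduled biopsy visit window. For Week 48 this could be the end of the Week 52 visit window (day 378) or the fifth dose, whichever is earlier. Close Week 74 in the same way, before any sixth dose and before the Week 96 visit window.
2. State that this date rule overrides the CRF-visit sentence for the histology and HPV endpoints.
3. State that a subject with no sample in the closed window lacks the Week 48 endpoint and is handled under the existing mITT definition in section 2.1.

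Counting such subjects as non-responders would be a separate decision. It would change the primary population, and sections 2.1 and 3.1 would have to be aligned with it.

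The cost is a few sentences of wording. A few late samples would no longer count, and a biopsy taken more than 14 days early would stay outside the window, as it already does under the date rule. The sample size of 36 and the critical counts (2 of 10 to 11, 3 of 21 to 22) are unchanged.
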